## Study Summary

Title	Novel Interventions for Alcohol Dependent Frequent Emergency Department Users: A phase IV, randomized, open-label, non-placebo-controlled, single-center study of the feasibility, acceptability, and effect of extended-release naltrexone 380mg intramuscular injection compared to standard care on healthcare utilization, drinking, and quality of life in subjects with severe alcohol use disorders and frequent emergency department use.
Short Title	XR-NTX in ED users with AUDs
Protocol Number	S13-00928
Phase	4
Methodology	Randomized, Open Label, non-placebo (compared to standard care)
Study Duration	8 years
Study Center(s)	Single-center
Objectives	To conduct a feasibility and acceptability study of XR-NTX+CM treatment in alcohol dependent patients with frequent ED use and explore its effect on healthcare utilization, drinking, and quality of life.
Number of Subjects	300 (Pilot, N=50; Subsequent trial N=250)
Diagnosis and Main Inclusion Criteria	Alcohol use disorder and frequent emergency department use
Study Product, Dose, Route, Regimen	Extended-release naltrexone (Vivitrol) 380mg intramuscular injection every 4 weeks
Duration of administration	12 months
Reference therapy	Reference is treatment as usual (No medications)
Statistical Methodology	Formal statistical analysis is not planned for the primary aim, in which we will a) further develop and pilot procedures and b) descriptively document feasibility and acceptability of XR-NTX for frequent ED users with alcohol use disorders. To explore the intervention effect, we will generate descriptive statistics and calculate changes in scores within and between groups.

CONFIDENTIAL

This material is the property of the NYU School of Medicine and Langone Medical Center. Do not disclose or use except as authorized in writing by the study sponsor

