project enrolling a total of 300 subjects in both phases. These estimates are founded in the current literature and the analyses, hypotheses, and predictions of experts in the field.

[name]'s ongoing study (R01AA020836) comparing the effectiveness of oral naltrexone to XR-NTX in alcohol dependent primary care patients has a targeted enrollment of n=117 in each of the two arms to detect a 20% absolute difference in primary clinical outcomes based in the Fisher's exact test with a projected power of 90%. [name], PhDs' (R01 AA022309) four-arm RCT of alcohol dependent homeless individuals recruited from a community housing program (XR-NTX + Counseling, Placebo + Counseling, Counseling alone, Treatment as Usual) will enroll a total of 300 patients (N=75/arm). This study population is similar to the one we will be studying.

A sample of 125 subjects per arm would allow us to detect a moderate effect size (Cohen's d of slightly less than 0.40) to provide power of 0.80 or greater at  $\alpha < .05$ . Another consideration when determining sample size is to power the study to detect the reduction in ED visits that would entirely offset the cost of medication. The institutional costs of a dose of Vivitrol (XR-NTX) is comparable to the estimated institutional cost of a single ED visit to Bellevue Hospital (according to the New York State Institute Cost Review). To detect a difference of  $\geq 6$  ED visits (i.e. a 6 month course of Vivitrol) between study arms comprised of subjects having a mean of  $22 \pm 15$  ED visits per year (per our pilot study data), would require 100 subjects per arm with  $\alpha = 0.05$ ;  $\beta = 0.20$  or, more conservatively, 133 subjects per arm with  $\alpha = 0.05$  and  $\beta = 0.10$ .

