### **Aim 2: Analysis of Effect:**

- a. We will explore the relative efficacy of XR-NTX+CM to standard care on decreasing acute healthcare use (ED, inpatient, other (ambulance, detoxification)) and associated expenditures.
- b. Secondarily, we will explore effects on healthcare engagement (clinic use, medication adherence, self-efficacy, motivation to change), alcohol quantity/frequency, alcohol-related consequences, quality of life measures, and cost-effectiveness.
- c. We will triangulate data sources for outcome measures to explore their correlation and to address missing data. Of specific interest, we will assess the performance of biomarkers (CDT and GGT, combinations) as an objective measure of changes in heavy drinking, which will inform the design of the second phase of study (definitive trial).

Although randomization would predict equal distribution of cofounders, we will examine their distribution and adjust accordingly. Interactions or confounding may occur between outcome domains (e.g. quality of life may have an effect on healthcare utilization); other cofounders may include age, race, sex, socioeconomic status, comorbidities, and social stability. See Figure 3.

We will ascertain healthcare utilization by triangulating data from subject self-report (Form 90) and from various other sources (pending availability), including Bellevue Hospital and New York City Health and Hospitals Corporation databases, partnering hospital medical records, EMS database of ambulance transports to all NYC EDs, and Medicaid claims data. We will report expenditures as reimbursement payments and/or using Medicaid payment rates as a cost proxy.

[figure not shown]

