We will use a mixed-methods approach with questionnaires and instruments (See 7.2.1) that are widely-used as well as database analyses to assess heavy drinking days and other substance use (TLFB, Form 90), craving (Penn Alcohol Craving Scale), self-efficacy (AASE), and quality of life (EQ-5D), consequences related to drinking (SIP-2R, Form 90), health and psychosocial status and utilization of services (Form 90). Changes in heavy drinking will also be assessed (secondarily) via analysis of biomarkers (CDT and GGT combinations will be tested); described below in Aim 2c (below). Multiple endpoint variables will not be normally distributed. We will generate descriptive statistics to characterize subjects, describe the distribution of baseline health and functioning, and calculate changes in severity scores. We will adopt a mixed methods approach to identify relationships between these variables. We will use independent t-tests or Wilcoxon rank-sum tests to compare pre-treatment variables of the two groups, and paired t-tests or Wilcoxon signed-rank tests to test pre- to post-treatment changes within each group. We will conduct an intention-to-treat analysis of healthcare use and expenditures for the 6- and 12-month periods before and after intervention using differences-in-differences multivariate linear regression modeling and repeated measures analysis. Correlations between the triangulated outcome measures will be assessed and inform the second phase of study.

Short-term estimates of costs and effectiveness will be obtained using a combination of pre-specified medical record and survey endpoints using methods described by [name] in his protocol # S12-

CONFIDENTIAL

This material is the property of the NYU School of Medicine and Langone Medical Center. Do not disclose or use except as authorized in writing by the study sponsor

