02263. Cost assessment will be conceptually similar to recently published analyses of the COMBINE interventions and will include medical and non-medical costs as well as payer and societal costs (Form 90). Effectiveness assessment will include alcohol consumption measures, quality of life, consequences, and the EQ-5D. The EQ-5D is among the most commonly used quality-of-life measure for informing cost-effectiveness analyses because it has minimal respondent burden, is well validated, and it yields utilities (preference-based measures on a scale of 0 to 1), the desired input for cost-effectiveness models. Because costs are skewed, incremental costs will be assessed using ordinary least squares and median regression models with covariates for treatment intervention and other relevant factors, and conditional models may be used because of cost data that may include “zeros.”

**Figure 3: The Predictor variables (study arms) are shown on the left and four outcome domains on the right (Healthcare utilization, Drinking, Quality of Life, and Consequences) with the specific measures noted alongside each domain. The outcomes may be mediated by the subjects' development of engagement (assessed by AASE scale, motivation visual analogue scale, adherence to treatment arm, and participation in clinic). Several potential interactions are hypothesized, some of which may also act as confounders. Interactions or confounding may occur between outcome domains (e.g. quality of life may have an effect on healthcare utilization); other cofounders may include age, race, sex, socioeconomic status, comorbidities, and social stability. Randomization will be employed to help mitigate potential threats.**

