We will collect patient-level characteristics data to explore the association of patient-level characteristics (e.g. sex, race) with effectiveness. We will be able to carefully track prior detox admissions and concurrent 12-step and specialty alcohol treatment involvement in the proposed trial in order to estimate associations with treatment effectiveness. Multivariate models will be used to identify patient characteristics associated with treatment success. The analysis will utilize a logistic regression with an indicator variable for treatment and covariate terms for baseline potential prognostic indicators, including African American ethnicity, baseline drinking severity, and status of housing, social support, quality of life, and OPRM1 genotype. Odds ratios will be calculated to quantify the risk to treatment failure of significant predictors. As originally proposed, naltrexone appears most effective at reducing heavy drinking, as opposed to producing complete abstinence. A harm reductionist perspective delineating treatment success from failure is particularly important in this population having a greater severity of AUD and psychosocial dysfunction. All traditional alcohol treatment trial clinical endpoints, including continuous

CONFIDENTIAL

This material is the property of the NYU School of Medicine and Langone Medical Center. Do not disclose or use except as authorized in writing by the study sponsor

drinking and heavy drinking variables, as well as the %CDT biomarker, the change in CDT, and the combined CDT-GGT equation, which are specific for heavy drinking, are of great interest, and will be reported.

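### For drinking, craving, SIP-2R and EQ-5D scores, the only tests of change that Aim 2 states are paired tests within each arm

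*Combined protocol and SAP*

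**What the plan says.** Section 7.2.2, Aim 2, ties each named method to a purpose:

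- Baseline: "independent t-tests or Wilcoxon rank-sum tests to compare pre-treatment variables of the two groups".
- Change: "paired t-tests or Wilcoxon signed-rank tests to test pre- to post-treatment changes within each group".
- Healthcare use and expenditures: intention-to-treat difference-in-differences regression and repeated measures analysis.
- Costs: ordinary least squares and median regression with a treatment covariate.

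Item b of Aim 2 puts these under the analysis of effect: "alcohol quantity/frequency, alcohol-related consequences, quality of life measures, and cost-effectiveness". The Figure 3 caption makes study arm the predictor of the drinking, quality-of-life and consequences domains. Craving is listed among the Aim 2 measures.

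Five other places come close to a between-arm analysis of these scores:

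- The Study Summary says the team will "generate descriptive statistics and calculate changes in scores within and between groups". It names no test, model or visit.
- Aim 2 says "Short-term estimates of costs and effectiveness will be obtained using a combination of pre-specified medical record and survey endpoints", using the methods of another protocol (S12-02263), and adds "Effectiveness assessment will include alcohol consumption measures, quality of life, consequences, and the EQ-5D". Craving is not in that list.
- Sections 3.3 and 7.2.1 say analyses will resemble those of other naltrexone studies. Their methods are not given here.
- Aim 2c has a repeated-measures ANOVA, but for biomarkers, and the outcome groups it compares are not defined.
- Aim 3 says "The analysis will utilize a logistic regression with an indicator variable for treatment". Its outcome is treatment success or failure, with no stated cut-off.

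**The concern.** Aim 2 asks whether the intervention changes these scores relative to standard care. A paired test asks whether one arm moved from its own baseline, and two such tests side by side do not estimate the difference between arms.

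This matters in this population. Section 4.1, criterion 6, admits subjects on current heavy drinking (at least 2 days a week), so drinking scores may fall in both arms without any treatment effect. Section 7.1 makes the same point about earlier case-management studies, saying most were uncontrolled and overstated their effect through regression to the mean. Paired tests within arms leave the randomised control unused for these scores.

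In phase 1 the stakes are modest, because section 2 calls the initial Aim 2 analysis exploratory. They are higher in phase 2. The same protocol covers all 300 subjects, and section 7.1 projects 125 per arm as a definitive test on multiple outcomes.

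**Working it through.** **Step 1. The plan's own figures (section 7.1).** Two-sample t, two-sided alpha 0.05 (sidedness assumed), 1:1 allocation.

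- 125 per arm, 80% power: detectable d = 0.356. This agrees with the stated value of slightly under 0.40.
- A difference of 6 ED visits with SD 15 is 6/15 = 0.40 SD. The required n is 99.1 at 80% power and 132.3 at 90%, rounding up to the stated 100 and 133 per arm.

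The figures reproduce, and both are between-arm calculations. The d is not tied to a named outcome. The ED-visit calculation has a matching between-arm model in Aim 2; these scores do not.

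**Step 2. What within-arm p-values would show with no treatment effect.** The documents give neither a common change nor a before/after correlation for these scores, so both are assumed. The common fall f is 0, 0.2 or 0.4 SD, the correlation rho is 0.3, 0.5 or 0.7, and there is no missing data. The sizes are 125 per arm (section 7.1) and 25 per arm (50 pilot subjects in two arms).

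- Standardised paired change: f / sqrt(2(1 − rho)). For f = 0.2 this is 0.169, 0.200 and 0.258.
- Let p be the power of the paired t-test at that value (noncentral t, two-sided 0.05).
- The arms are independent, so P(exactly one significant) = 2p(1 − p) and P(both) = p².

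| n per arm | f | rho | p | exactly one arm | both arms |
|---|---|---|---|---|---|
| 25 | 0.2 | 0.3 | 0.128 | 0.224 | 0.016 |
| 25 | 0.2 | 0.5 | 0.161 | 0.269 | 0.026 |
| 25 | 0.2 | 0.7 | 0.236 | 0.361 | 0.056 |
| 125 | 0.2 | 0.3 | 0.466 | 0.498 | 0.217 |
| 125 | 0.2 | 0.5 | 0.602 | 0.479 | 0.363 |
| 125 | 0.2 | 0.7 | 0.817 | 0.299 | 0.668 |
| 125 | 0.4 | 0.3 | 0.963 | 0.071 | 0.928 |
| 125 | 0.4 | 0.5 | 0.993 | 0.013 | 0.987 |
| 125 | 0.4 | 0.7 | 1.000 | 0.000 | 1.000 |

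With f = 0, p = 0.05 and exactly one arm is significant in 2 × 0.05 × 0.95 = 9.5% of trials at either size.

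**Step 3. The between-arm alternative.** In simulation under the same null with f = 0.2 (8,000 trials per cell), a baseline-adjusted between-arm test rejected in 4.6% to 5.3% of trials across both sizes and all three correlations.

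The 95% confidence half-width of the adjusted difference is t × sqrt(2(1 − rho²)/n). For rho = 0.3, 0.5 and 0.7 this is 0.54, 0.49 and 0.41 SD at 25 per arm, and 0.24, 0.22 and 0.18 SD at 125.

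**The case against.** The strongest defence is that this is an exploratory secondary aim. The Study Summary lists between-group changes as well as within-group ones, and the plan points to sister studies whose protocols may contain a suitable model. Section 7.1 says phase 1 will inform the phase 2 power analysis, and section 15.1 says phase 2 funding is still to be sought, so the analysis could yet be revised.

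Much of this stands for phase 1. It does not close the gap for phase 2: no section says that 7.2.2 will be rewritten, and phase 2 enrols under this protocol. The cited methods cannot be checked from these documents. The only test reported for the study behind S12-02263 is in section 7.1, which sizes it "to detect a 20% absolute difference in primary clinical outcomes based in the" Fisher's exact test. That is a test of proportions, not of scores.

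A reader might infer four stronger claims, none of which the documents support:

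- That Aim 2 has no between-arm analysis at all. Healthcare use, expenditures and costs have one.
- That no between-arm comparison of these scores was intended. The Study Summary and Figure 3 show that it was; what is missing is a stated method.
- That section 7.1 sizes phase 2 on these scores. Its d names no outcome.
- That the plan carries a 30% to 50% false-positive rate. The plan never says arm-specific p-values will be taken as the treatment effect, and the percentage depends on the assumed fall.

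**Conclusion.** The point holds as a specification gap limited to drinking, craving, SIP-2R and EQ-5D scores. Paired tests within each arm are the only tests of change stated for them in Aim 2, and they cannot deliver the arm effect that Aim 2 asks for. It should be fixed before phase 2; on phase 1 alone it would be minor.

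The percentages show what could happen if arm-specific p-values were read as the effect. They do not measure an error in the plan. The share of trials with exactly one significant arm is 9.5% with no common fall and peaks near 50%. At a 0.4 SD fall and 125 per arm the picture changes: both arms are significant in 93% to 100% of trials, so the tests would report improvement in both arms with no treatment effect present.

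**What to change.** In section 7.2.2, Aim 2, state for these four groups of scores:

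- The effect analysis is a between-arm comparison adjusted for the baseline value. One suitable form is a mixed model on months 3, 6 and 12 with arm, visit, arm-by-visit and baseline.
- Use robust standard errors, since Aim 2 expects non-normal endpoints, with a small-sample correction at 25 per arm. In a simulation with assumed exchangeable correlation of 0.5, uncorrected robust errors rejected a true null in 5.9% of trials with complete data, and in 7.6% to 8.2% with 30% to 50% of visits missing at random.
- Name one visit in advance as the main contrast. Month 6 is an example, being the treatment period section 5.2 plans for every intervention subject.
- State how late or early assessments are allocated to visits. Section 6 allows 28 days before to 90 days after the due date, and catch-up assessments until 6 months after the week-48 visit.
- Report the estimate and confidence interval in phase 1, and use the named contrast as the test in phase 2. Keep within-arm changes as description only.
- If S12-02263 is meant to govern these scores, write its between-arm method into 7.2.2.

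The cost is a few sentences, including the visit-allocation rule, and a little more analysis work. Section 7.2.1 already schedules data collection at enrollment and months 3, 6 and 12, so no new data are needed.

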## 7 Statistical Plan

### 7.1 Sample Size Determination

Naltrexone has not demonstrated a robust treatment effect; however, most studies did not use the XR-preparation, are limited by poor adherence, and did not include this higher-severity population or other intervention components. We do not know what the “ideal” population for XR-NTX is, but posit that it may have a greater effect size in this more severely affected population than amongst the higher socioeconomic status population historically targeted. A recent pilot of XR-NTX suggests a possible greater effect (and acceptability) in a population similar to ours. Our literature search yielded no studies of initiating pharmacotherapy for alcohol dependence in the ED. There are only limited data on XR-NTX effects on several long-term outcomes of interest, including healthcare use, treatment engagement, and quality of life measures. ED-based case management studies demonstrate promising healthcare utilization outcomes, but most were uncontrolled and overestimated effect because of regression to the mean. The heterogeneity in study designs, interventions, and cohort characteristics precludes meta-analysis.

Determining sample size is challenged by limitations in the existing data and heterogeneity of populations. Definitively testing the relative effects of intervention components may require additional arms with as many as 75 to 200 subjects in each. Thus, we chose to start with the strongest intervention and compare it to standard care to maximize the likelihood of seeing an effect and of exploring effect size on various outcomes. The 2-arm design will minimize the loss of power and allow us to focus on the primary goal of assessing feasibility.

The first phase of study will be a feasibility and acceptability study, through which we will obtain preliminary data to inform the power analysis for the subsequent definitive trial. In the first phase, we plan to pilot the study in 50 subjects. In the second phase of study, we project enrolling 125 subjects in each of the two arms to definitively test the intervention’s effect on multiple outcomes of interest. Thus, we

CONFIDENTIAL

This material is the property of the NYU School of Medicine and Langone Medical Center. Do not disclose or use except as authorized in writing by the study sponsor

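### Healthcare use is to be analysed by linear difference-in-differences with no named adjustment for pre-period use; naming that covariate is a free gain in precision, mainly for phase 2

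*Combined protocol and SAP*

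**What the plan says.** Section 7.2.2, Aim 2, covers both utilisation and spending in one sentence, by intention to treat. The analysis is to run "for the 6- and 12-month periods before and after intervention using differences-in-differences multivariate linear regression modeling and repeated measures analysis". The model is not written out. Pre-period use is not named as a covariate, and neither window is called primary.

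On adjustment in general, the same section says: "Although randomization would predict equal distribution of cofounders, we will examine their distribution and adjust accordingly". The possible confounders it lists are age, race, sex, socioeconomic status, comorbidities and social stability. Baseline utilisation is not among them.

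A later paragraph of Aim 2 plans ordinary least squares and median regression for incremental costs, with covariates for treatment and other relevant factors. Those factors are not named.

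Section 7.1 takes a difference of 6 ED visits between arms, with a mean of 22 and SD of 15 visits per year from the pilot. It concludes that this "would require 100 subjects per arm" at alpha 0.05 and beta 0.20, or 133 per arm at beta 0.10. For phase 2, "we project enrolling 125 subjects in each of the two arms". No correlation between pre- and post-period visits, and no SD of change, appears anywhere.

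**The concern.** Difference-in-differences is a natural choice when the groups are not comparable at the start. Section 1.1 describes such a study: the earlier care-management pilot had non-equivalent controls. Here the arms are randomised (section 4.3.5), so baseline differences are due to chance and need no differencing to remove bias. What remains is a question of precision. A plain difference-in-differences subtracts the whole pre-period count, which fixes its coefficient at 1. A model with the pre-period count as a covariate estimates that coefficient from the data.

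Two things are at stake. The effect estimate may be less precise than the same data allow. And the power stated in section 7.1 belongs to a different analysis, so it does not tell the reader what the planned model will deliver in phase 2.

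**Working it through.** **Inputs.** From section 7.1: difference 6 visits, SD 15, alpha 0.05, power 0.80 and 0.90, 125 per arm in phase 2. Assumed: a two-sided test, equal SD in both periods and both arms, and rho over a range, since the documents give none.

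**Step 1: the plan's own figures.** The standardised difference is 6/15 = 0.40. A two-sided, two-sample t-test needs 99.1 per arm for 80% power and 132.3 for 90%. Rounded up, these are the stated 100 and 133. (The normal approximation gives 99 and 132. One-sided gives 78 and 108, which does not match.) The stated figures are therefore those of an unpaired comparison of one period's visits. At 125 per arm that test has 88.5% power for 6 visits.

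**Step 2: SD under each analysis.**
- Unadjusted change score: 15 × √(2(1 − rho))
- Follow-up count adjusted for pre-period count: 15 × √(1 − rho²)
- Variance ratio, adjusted to change score: (1 − rho²) / (2(1 − rho)) = (1 + rho)/2
- Information lost by the change score: 1 − (1 + rho)/2 = (1 − rho)/2

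Simulated variance ratios (125 per arm, 3,000 runs) were 0.66, 0.76 and 0.85 at rho 0.3, 0.5 and 0.7, against 0.65, 0.75 and 0.85 from the formula.

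**Step 3: power for 6 visits at 125 per arm, and number per arm for 80% power** (normal approximation).

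| rho (assumed) | SD change / adjusted | Information lost | Power change / adjusted | n per arm change / adjusted |
|---|---|---|---|---|
| 0 | 21.21 / 15.00 | 50% | 60.9% / 88.5% | 197 / 99 |
| 0.2 | 18.97 / 14.70 | 40% | 70.5% / 89.8% | 157 / 95 |
| 0.3 | 17.75 / 14.31 | 35% | 76.2% / 91.2% | 138 / 90 |
| 0.35 | 17.10 / 14.05 | 32.5% | 79.2% / 92.2% | 128 / 87 |
| 0.4 | 16.43 / 13.75 | 30% | 82.3% / 93.2% | 118 / 83 |
| 0.5 | 15.00 / 12.99 | 25% | 88.5% / 95.5% | 99 / 74 |
| 0.6 | 13.42 / 12.00 | 20% | 94.2% / 97.7% | 79 / 63 |
| 0.7 | 11.62 / 10.71 | 15% | 98.3% / 99.3% | 59 / 51 |
| 0.9 | 6.71 / 6.54 | 5% | above 99% / above 99% | 20 / 19 |

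**Step 4: where the change score meets the stated power.** It needs 99.1 × 2(1 − rho) per arm for 80% power. Setting this to 125 gives rho = 1 − 125/198.2 = 0.37. Its SD equals 15, the sized value, when 2(1 − rho) = 1, that is rho = 0.5. Below 0.5 it does worse than the sized test and above 0.5 it does better. The adjusted model does at least as well as the sized test at every rho, apart from the one degree of freedom spent on the covariate.

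**The case against.** The strongest reply is that the sentence in section 7.2.2 is open. It says multivariate and also mentions repeated measures. If the pre-period count is entered in a change-score regression, the treatment estimate is identical to that of the adjusted follow-up model; the simulation confirmed this. A repeated-measures model with a common baseline mean is about as efficient. This stands: the loss applies only to the unadjusted reading. But the plan commits to no efficient version and ties adjustment to observed imbalance. In an open-label trial (section 5.8) that choice is better fixed beforehand.

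A reader might infer that the trial is underpowered. The documents do not support that. Underpowering needs a low rho, and none is given. Selection on prior visits under section 4.1 is weak evidence for one: the criterion asks for only 3 visits in 12 months (and 6 in 24), against a mean of 22. In a negative binomial with mean 22 and SD 15 only about 2.5% fall below 3, and cutting them off moves rho from 0.305 to 0.301 or from 0.505 to 0.499. Section 1.1 says the case-finding algorithm looks for patients whose use is less likely to decline, which points towards persistence. The remark in section 7.1 that "most were uncontrolled and overestimated effect because of regression to the mean" concerns earlier case-management studies and does not give this trial's rho.

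The analysis is also secondary and exploratory in phase 1 (sections 2 and 3.3). Section 7.1 says of that phase that "we will obtain preliminary data to inform the power analysis for the subsequent definitive trial", so the missing quantities can be estimated in time. The 6-visit calculation is one of two sizing arguments, beside a general Cohen's d. All this lowers the urgency. It does not remove the reason to specify the model, since phase 2 is meant to be definitive and section 7.2.2 is the only effect plan given.

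**Conclusion.** The point holds as one of precision and specification, not of validity. Difference-in-differences is unbiased here. Read as an unadjusted change score, it gives up (1 − rho)/2 of the information that baseline adjustment would keep: 35%, 25% and 15% at assumed rho of 0.3, 0.5 and 0.7. No single figure can be claimed, because rho is not in the documents. Equal variances are also assumed; if the intervention lowers both the mean and the spread of visits, the exact ratios will shift.

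The figures in section 7.1 are correct for what they compute, a single-period comparison, but they do not describe the planned model. At 125 per arm the shortfall below 80% power for 6 visits arises only if rho is under about 0.37. Above 0.5 the planned model does better than stated. This is a free improvement, relevant mainly to phase 2.

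**What to change.** In section 7.2.2, Aim 2:
- Make the main effect model for healthcare use the follow-up count on arm plus the pre-randomisation count over a period of the same length. Use a linear model with robust standard errors, so that the result stays in visits and can be set against the 6-visit target.
- State whether the 6- or the 12-month window is primary.
- Keep difference-in-differences and a negative binomial model as sensitivity analyses.
- In the cost regressions, name pre-period expenditure as a covariate.

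In section 7.1, state that 100 and 133 per arm refer to a single-period comparison. Base the phase 2 power calculation on the adjusted model, with rho and SD estimated from phase 1. Fifty subjects will estimate rho only roughly, so show power over a range. The adjusted model is forgiving here: at 125 per arm with SD 15 its power for 6 visits runs from 88.5% at rho 0 to 99.3% at rho 0.7.

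The cost is wording only. The planned difference-in-differences already needs the same pre-period visits and expenditures, so no new data are required.
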